5.2.3. Exploratory Exposure Response Analyses

Summaries of plasma concentrations of peramivir will be presented by time point and age group. Scatter plots will be generated for time to alleviation of influenza symptoms and change from baseline in \log_{10} TCID₅₀/mL versus peramivir plasma concentration at 30-60 minutes following study drug administration. The data from this trial together with data from prior trials may be used to complete a separate exposure-response analysis. The methods for the exposure-response analysis will be presented in a separate Statistical Analysis Plan.

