**6.2. Secondary Objectives**

- To describe the pharmacokinetics of IV peramivir in elderly and high risk subjects with acute uncomplicated influenza.
- To evaluate the effectiveness of IV peramivir in elderly and high risk subjects with acute uncomplicated influenza.
- To evaluate the incidence of influenza complications, specifically otitis media, sinusitis, bronchitis or pneumonia requiring antibiotic use diagnosed after initiation of treatment

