  - e. History of blood dyscracias including sickle cell anemia and thalassemia
  - f. History of renal impairment (creatinine clearance [CrCl]  $<$  50 mL/min as determined by the Cockcroft-Gault formula) ([Cockcroft and Gault 1976](#)), including dialysis.

- g. History of liver disease including cirrhosis
  - h. Mild to moderate immunocompromise, including: history of HIV disease on stable HAART with last known CD4+ count  $\geq 200$  cells/ $\mu$ L; known neutropenia with ANC  $> 500$  cells/ $\mu$ L; chronic corticosteroid use of  $< 20$  mg/d for any indication.
  - i. History of diabetes mellitus
  - j. Morbid obesity (body mass index [BMI]  $\geq 40$ )
  - k. American Indian or Alaskan native
5. Written informed consent

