## 9. TREATMENT OF SUBJECTS

### 9.1. Study Drug Dose Rationale

Subjects will be dosed with peramivir at the dosage levels currently approved in the US package insert for peramivir. The standard dose will be a single IV dose of 600 mg for subjects with CrCL  $\geq$  50 ml/min and reduced for subjects with CrCL < 50 ml/min as described in Section 9.4.

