**Table 2. Dosage Adjustment for Subjects with Altered Creatinine Clearance**

	Creatinine Clearance (mL/min) a		
	$\geq$ 50	30 to 49	10 to 29
Recommended Dose (mg)	600 mg	200 mg	100 mg

a Calculated using the Cockcroft -Gault equation.

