Table 14.3.4.1.1	Summary of Chemistry Laboratory Values by Study Visit: Safety Population
Table 14.3.4.1.2	Summary of Hematology Laboratory Values by Study Visit: Safety Population
Table 14.3.4.2	Graded Laboratory Toxicities: Safety Population
Table 14.3.4.3.1	Laboratory Shifts from Baseline to Day 7 - Chemistry: Safety Population
Table 14.3.4.3.2	Laboratory Shifts from Baseline to Day 7 - Hematology: Safety Population
Table 14.3.4.3.3	Laboratory Shifts from Baseline to Day 7 - Urinalysis: Safety Population
Table 14.3.5	Study Drug Exposure: Safety Population
Table 14.3.6	Summary of Vital Signs by Study Visit: Safety Population
Table 14.3.7.1	Concomitant Medications by Generic Name and Drug Classification: Safety Population
Table 14.3.7.2	Antipyretic Concomitant Medications by Generic Name and Drug Classification: Safety Population
Table 14.3.7.3	Concomitant Medications Used to Treat Influenza Symptoms by Generic Name and Drug Classification: Safety Population
Table 14.4.1.1	Summary of Plasma Concentrations of Peramivir by Time Point: Intent-to-Treat Population
Table 14.4.1.2	Summary of Plasma Concentrations of Peramivir by Time Point: Exposure-Response Population
Figure 14.4.2	Relationship between Time to Alleviation of Influenza Symptoms and Peramivir Plasma Concentrations at 30-60 Minutes Post-Dose: Exposure-Response Population

Output Number	Output Title
Figure 14.4.3	Relationship between Viral Change from Baseline and Peramivir Plasma Concentrations at 30-60 Minutes Post-Dose: Exposure-Response Population
Listing 16.2.1	Study Completion: Intent-to-Treat Population
Listing 16.2.2	Protocol Deviations: Intent-to-Treat Population
Listing 16.2.4.1	Inclusion/Exclusion Criteria: Intent-to-Treat Population
Listing 16.2.4.2	Subject Eligibility: Intent-to-Treat Population
Listing 16.2.4.3	Demographics: Intent-to-Treat Population
Listing 16.2.4.4	Medical History: Intent-to-Treat Population
Listing 16.2.4.5	Prior and Concomitant Medications: Intent-to-Treat Population
Listing 16.2.5.1	Study Medication Administration: Intent-to-Treat Population
Listing 16.2.5.2	Pharmacokinetic Sample Collection Time and Concentrations: PK Population
Listing 16.2.6.1.1	Summary of Efficacy Variables: Intent-to-Treat-Infected Population
Listing 16.2.6.2	Influenza Symptoms: Intent-to-Treat Population
Listing 16.2.6.3	Temperature: Intent-to-Treat Population

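### The SAP's peramivir concentration tables and exposure-response plots neither split nor mark the 600, 200 and 100 mg doses, so they can reflect dose mix as well as pharmacokinetics

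*SAP*

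**What the plan says.** One secondary objective in Protocol 6.2 reads: "To describe the pharmacokinetics of IV peramivir in elderly and high risk subjects with acute uncomplicated influenza".

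Protocol 9.1 sets 600 mg as the standard dose, "reduced for subjects with CrCL < 50 ml/min as described in Section 9.4". Table 2 in Section 9.4 gives the levels: "Recommended Dose (mg) 600 mg 200 mg 100 mg", for CrCl of at least 50, 30 to 49 and 10 to 29 mL/min. CrCl comes from the Cockcroft-Gault equation in Appendix 1, which contains the term (140 - age). Protocol 8.1 makes a history of CrCl below 50 mL/min, dialysis included, one of the qualifying risk factors.

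SAP 5.2.3 plans two kinds of output:
- Tables: "Summaries of plasma concentrations of peramivir will be presented by time point and age group". SAP 5 defines the age groups as under 65, 65-75, over 75, and 65 or older.
- Scatter plots of time to alleviation and of change in viral titer, each "versus peramivir plasma concentration at 30-60 minutes following study drug administration".

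The output list in SAP 9 matches. Table 14.4.1.1 is the "Summary of Plasma Concentrations of Peramivir by Time Point: Intent-to-Treat Population", Table 14.4.1.2 repeats it for the exposure-response population, and Figures 14.4.2 and 14.4.3 are the plots. None of the titles mentions dose. SAP 8 says group headers identify the age group. Neither dose nor CrCl is a grouping factor in SAP 3.3.2, 5, 5.2.4 or 5.3.4. The SAP acknowledges reduced dosing only in its study overview (1.1).

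**The concern.** Doses differ up to 6-fold, and the rule that assigns them depends partly on age, the SAP's main grouping factor. A mean taken across 600, 200 and 100 mg describes neither the full-dose nor the dose-reduced subjects in an age group. If the dose mix differs between age groups, mean concentrations can differ with no difference in pharmacokinetics, or a real difference can be masked.

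The plots raise a related problem. Dose-reduced subjects tend to have low 30-60 minute values because less drug was given, but the reduction follows from their lower renal function. Total exposure is dose divided by clearance. As an illustration, a third of the dose with a third of the clearance gives the same total exposure from an early level about one third as high. A low early value can therefore mark renal impairment, and for those subjects it is a poor proxy for low total exposure.

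**Working it through.** The plan states no figure to reproduce. There is no PK precision target, no hypothesis test, and no expected share of dose-reduced subjects. The steps below are illustrations on stated assumptions.

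**1. Can age move a subject across the dose cut?** The formula is Appendix 1; weight 70 kg and serum creatinine 1.0 mg/dL are assumed. For a woman, CrCl = (140 - age) x 70 x 0.85 / 72.
- Age 65: 75 x 59.5 / 72 = 62.0 mL/min
- Age 75: 65 x 59.5 / 72 = 53.7 mL/min
- Age 80: 60 x 59.5 / 72 = 49.6 mL/min

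The last falls below 50 with weight and creatinine unchanged.

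**2. Effect on a pooled mean.** Assume early concentration is proportional to dose. Let f200 and f100 be the shares of an age group given 200 and 100 mg. The shortfall against the 600 mg mean is f200 x (1 - 200/600) + f100 x (1 - 100/600) = f200 x 2/3 + f100 x 5/6.

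| Assumed f200 / f100 | Shortfall in mean | Shortfall if dose-normalised level is 1.5 times higher in the impaired |
|---|---|---|
| 10% / 0% | 6.7% | 5.0% |
| 20% / 5% | 17.5% | 13.75% |
| 30% / 10% | 28.3% | 22.5% |

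The last column uses 1 - [(1 - f200 - f100) + 1.5 x (f200/3 + f100/6)].

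The median moves less. Assume a lognormal distribution with a 30% within-dose CV and every reduced-dose value below the 600 mg values. With f = f200 + f100, the pooled median is then the (0.5 - f)/(1 - f) quantile of the 600 mg distribution. The shortfalls are about 4%, 12% and 25%.

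**3. Effect on spread.** With the same 30% within-dose CV, shares of 20%/5% give a pooled mean of 0.825 and a variance of 1.09 x (0.75 + 0.20/9 + 0.05/36) - 0.825² = 0.163. The pooled CV is √0.163 / 0.825 = 49%.

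**4. Effect on an age contrast.** Suppose there is no PK difference between two groups, one with shares 10%/0% and the other 20%/5%. The ratio of means is 0.825 / 0.933 = 0.88. If the older group has the larger reduced-dose share, it appears 12% lower. If the younger group has it, the older group appears 13% higher (0.933 / 0.825 = 1.13).

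**5. Effect on the plots.** Assume no exposure-response relation within a dose, a share f given 200 mg, a within-dose SD of log concentration of 0.3, and log recovery time d SD longer in dose-reduced subjects. Then

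correlation = -f(1-f) d ln3 / √{[0.09 + f(1-f)(ln3)²] [1 + f(1-f)d²]}.

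| d | f = 10% | f = 20% | f = 30% |
|---|---|---|---|
| 0 | 0 | 0 | 0 |
| 0.5 | -0.11 | -0.16 | -0.19 |
| 1.0 | -0.21 | -0.31 | -0.36 |

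A spurious trend needs d to differ from zero.

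**The case against.** The strongest reply is that these outputs are not the main PK analysis. The protocol synopsis plans a mixed-effects population PK analysis with covariates, estimated separately for subjects 65 or older and for younger high-risk subjects. Such a model takes administered dose as an input. SAP 1 places PK in a separate report, and SAP 6 anticipates no further change to protocol-specified analyses, so the model has not been withdrawn. This stands. A reader might infer that the PK objective for the elderly fails, or that these tables are the only PK results certain to appear; the documents support neither. The word may in SAP 5.2.3 governs only the separate exposure-response analysis.

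Three further points also stand:
- Subjects under 65 can enter because of renal impairment. A reader might infer that any age difference in the tables is a dose-mix effect, or that the elderly will look lower; neither is established.
- Achieved concentration is the proper axis for an exposure-response plot. A reader might infer that dose-reduced subjects are misplaced 3- or 6-fold to the left, but dose-normalising that axis would plot concentrations nobody had. What remains is weak proxy value and possible confounding. The documents give no evidence on whether renal function affects recovery.
- The section is headed exploratory, nothing is tested, and Listings 16.2.5.1 and 16.2.5.2 would allow a later dose split.

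None of this repairs the tables and plots that the SAP does specify. Produced as written, they mix doses without telling the reader.

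**Conclusion.** The point holds for SAP 5.2.3, Tables 14.4.1.1-14.4.1.2 and Figures 14.4.2-14.4.3. Pooling is inferred from the absence of any dose split; the SAP does not state it.

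For an age group with the assumed reduced-dose shares, the pooled mean lies about 7% to 28% below the 600 mg mean under dose proportionality. It lies about 5% to 22.5% below if dose-normalised levels are 1.5 times higher in the impaired. The actual shares are not in the documents, so the real size is unknown and the direction of any age contrast is not fixed. For the plots, a trend could be confounded only if renal function or age also relates to recovery; a false trend is possible, not predicted.

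The population PK model mitigates the problem for the secondary PK objective, and the primary safety endpoint is not affected. This is a worthwhile correction to descriptive outputs, not a flaw in the trial's main conclusions.

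**What to change.** In SAP 5.2.3 and the table and figure shells:
- **Tables 14.4.1.1-14.4.1.2:** summarise concentrations by dose received (600, 200, 100 mg) within age group.
- **Added summary:** give concentrations normalised to 600 mg by age group and by CrCl category (at least 50, 30-49, 10-29 mL/min). Show subjects below 10 mL/min or on dialysis separately; they can be enrolled, and the Table 2 bands stop at 10.
- **Figures 14.4.2-14.4.3:** keep achieved concentration on the axis and mark each point by dose. Add a 600 mg-only version as a supplement; as the main plot it would drop one of the target risk groups.
- **Table 14.3.5:** show dose received by age group. SAP 5.3.4 does not list the exposure items exhaustively, so dose may already be intended; it should be named.

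The cost is SAP wording and table shells. CrCl is calculated at screening (Protocol 11.2.1), and drug administration and concentrations are already listed. The drawback is small cells in the 200 and 100 mg strata, which is acceptable in a descriptive study if the counts are shown.

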5.2.4. Subgroup Analyses

The effectiveness analyses will also be presented by viral subtype determined at Screening.

5.3. SAFETY

5.3.1. Adverse Events

AEs will be mapped to a Medical Dictionary for Regulatory Activities (MedDRA) version 18.0 preferred term and system organ classification. If a subject experiences multiple events that map to a single preferred term, the greatest severity grade and strongest investigator assessment of relation to study medication will be assigned to the preferred term for the appropriate summaries. Should an event have a missing severity or relationship, it will be classified as having the highest severity and/or strongest relationship to study medication. An overall summary of TEAEs will be generated, showing the number of subjects with at least one AE, SAE, AE related to study drug, AE leading to discontinuation of study, SAE related to study drug, severe or life-threatening AE, and severe or life-threatening AE related to study drug. Summaries of TEAEs will include any AEs reported beginning with the initiation of study drug on Day 1. The occurrence of TEAEs will be summarized by age group using preferred terms, system organ classifications, and severity. Separate summaries of TEAEs, treatment-emergent SAEs, TEAEs related to study drug, events

leading to the discontinuation of study, and events leading to the discontinuation of study drug will be generated by preferred term and system organ classification. TEAEs occurring in $\geq 10\%$ of subjects will be summarized by preferred term. All AEs reported will be listed for individual subjects showing both verbatim and preferred terms. A separate listing of all SAEs will be generated. All AEs that occurred prior to the initiation of study treatment or more than 14 days post-study drug discontinuation will be excluded from the tables but will be included in the listings.

Missing onset dates will be imputed as previously outlined in Section 3.3.5 as required to determine whether AEs were treatment-emergent.

5.3.2. Concomitant Medications

Prior and concomitant medications, as well as symptom relief medications recorded on the subject diary, will be coded using the World Health Organization (WHO) drug dictionary (Version: March, 2015). All concomitant medications, antipyretic concomitant medications, and concomitant medications used to treat influenza symptoms will be summarized by frequency of drug classification and generic drug name. Prior and concomitant medications will be presented in a data listing. Symptom relief medications will be presented in a data listing.

5.3.3. Clinical Laboratory Assessments

Descriptive summaries of selected (quantitative) clinical laboratory results will be presented by study visit for each age group and overall. The clinical chemistry profile will include: albumin, alkaline phosphatase (ALP), alanine aminotransferase (ALT), aspartate aminotransferase (AST), bicarbonate, direct bilirubin, bilirubin, blood urea nitrogen, calcium, creatine kinase, chloride, creatinine, gamma glutamyl transferase, glucose, potassium, lactate dehydrogenase (LDH), magnesium, phosphate, protein, sodium, and urate. The hematology profile will include: basophils, basophils/leukocytes, eosinophils, eosinophils/leukocytes, hematocrit, hemoglobin, lymphocytes, lymphocytes/leukocytes, erythrocyte mean corpuscular hemoglobin, erythrocyte mean corpuscular hemoglobin concentration, erythrocyte mean corpuscular volume, monocytes, neutrophils, neutrophils/leukocytes, platelets, erythrocytes, and leukocytes. Laboratory abnormalities (toxicities) will be graded according to the Division of AIDS (DAIDS) Table for Grading Adverse Events for Adults and Pediatrics (Published Date: December 2004). The number and percentage of subjects who experience treatment-emergent toxicities will be summarized for each age group and overall. Laboratory toxicity shifts from baseline to Day 7 will be summarized for each age group and overall.

All laboratory toxicities that occurred before the initiation of study treatment or more than 14 days post study drug discontinuation will be excluded from the tables but will be included in the listings.

5.3.4. Other Safety Analyses

Exposure to study drug, including infusion time treatment status, will be summarized by age group

and overall.

Descriptive summaries of vital signs measured by study site personnel will be presented by study visit for each age group and overall.

All physical examination findings will be listed by age group and study visit.

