**Safety:**

Qualitative analyses will be performed for AE type, frequency and severity, as well as vital sign absolute values, clinical laboratory absolute values, and physical examination findings and their respective changes from Baseline for all subjects.

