## **7. INVESTIGATIONAL PLAN**

### **7.1. Endpoints**

#### **7.1.1. Primary Endpoint**

The primary endpoint of this study will be safety and include the assessment of AEs, laboratory abnormalities (clinical chemistry, hematology and urinalysis), vital signs and physical examinations.

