### **13.9. Safety Analyses**

Adverse Events will be mapped to a Medical Dictionary for Regulatory Activities (MedDRA)-preferred term and system organ classification. The occurrence of treatment-emergent AEs (TEAEs) will be summarized by age group and treatment group using MedDRA-preferred terms, system organ classifications, and severity. All AEs will be listed for individual subjects showing both verbatim and preferred terms. Separate summaries of treatment-emergent SAEs and AEs related to study drug will be generated.

Descriptive summaries of vital signs and clinical laboratory results will be presented by age group, treatment group and study visit. Laboratory abnormalities will be graded according to the DAIDS Table for Grading Adverse Events for Adults and Pediatrics (Publish Date: December 2004 Clarification, 2009, see Section 16.2). The number and percentage of subjects experiencing treatment-emergent graded toxicities will be summarized overall and by age group. Laboratory toxicity shifts from baseline to post-baseline assessments will be summarized overall and by age group.

Previous and concomitant medications will be mapped to a WHO preferred term and drug classification. The number and percent of subjects taking concomitant medications will be summarized using preferred terms and drug classifications.

The number and percent of subjects experiencing influenza related complications will be summarized overall and by age group.

Subject disposition will be presented for all subjects. The number of subjects who completed the study and discontinued from the study will be provided. The reasons for early discontinuation also will be presented.

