6. CHANGES IN THE PLANNED ANALYSES

An analysis of the number of doses of antipyretic medications will be prepared.

There are no further changes anticipated to the protocol specified analyses. Should any more deviations occur, these changes will be fully described in the Clinical and Statistical Report.

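### For vital signs and continuous laboratory values, the SAP plans only by-visit summaries and omits the change from baseline named in the protocol synopsis

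*SAP*

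**What the plan says.** Protocol 7.1.1 rests the study on safety: "The primary endpoint of this study will be safety and include the assessment of AEs, laboratory abnormalities (clinical chemistry, hematology and urinalysis), vital signs", with physical examinations completing the list. The safety paragraph of the synopsis, under statistical methods, names "vital sign absolute values, clinical laboratory absolute values, and physical examination findings and their respective changes from Baseline for all subjects".

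Protocol 13.9, the section that sets out the safety analyses, words it differently: "Descriptive summaries of vital signs and clinical laboratory results will be presented by age group, treatment group and study visit". It then adds graded toxicities and a categorical comparison with baseline for laboratory data: "Laboratory toxicity shifts from baseline to post-baseline assessments will be summarized overall and by age group". It does not name a continuous change from baseline.

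For vital signs, SAP 5.3.4 says "Descriptive summaries of vital signs measured by study site personnel will be presented by study visit for each age group and overall". For laboratory values, SAP 5.3.3 says "Descriptive summaries of selected (quantitative) clinical laboratory results will be presented by study visit for each age group and overall", and adds treatment-emergent toxicities and toxicity shifts from baseline to Day 7. SAP 3.3.8 gives a general definition of change from baseline. SAP section 6 declares one addition, a count of antipyretic doses, and then states "There are no further changes anticipated to the protocol specified analyses". SAP 5.4 gives the SAP precedence wherever it differs from the protocol.

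**The concern.** This is a single-arm study, so for vital signs and laboratory values the comparison with each subject's own baseline is the natural internal contrast. The synopsis names it, but no safety text or table title in the SAP calls for it on the continuous scale. Because the SAP prevails over the protocol, a programmer following it would not produce the analysis, and a reader of section 6 would not learn that it had gone.

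The loss is greatest in three places:

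- **Vital signs.** Table 14.3.6 is the only vital signs table. Nothing in it relates a subject's later reading to that subject's earlier one.
- **Laboratory movement that grades do not register.** This covers analytes with no DAIDS grade and changes that stay within a grade. Neutrophils show why it could matter: Protocol 5.3.1.2 reports decreased neutrophil count in 5.7% on peramivir 600 mg against 0.0% on placebo. The adult Grade 1 range in the protocol's DAIDS table starts at 1,300/mm³, so a fall from 6,000 to 1,400 would carry no grade.
- **Day 14 laboratory means.** These samples are repeated only when Day 7 is judged abnormal or changed, so a Day 14 mean and a Baseline mean describe different subjects.

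**Working it through.** The plan states no figure on this point, so there is none to reproduce. The check has four steps.

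**1. What each document provides**

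| Data | Protocol synopsis | Protocol 13.9 | SAP 5.3.3, 5.3.4 and section 9 |
|---|---|---|---|
| Vital signs | values and change | values by visit | values by visit (Table 14.3.6) |
| Laboratory, continuous | values and change | values by visit | values by visit (Tables 14.3.4.1.1, 14.3.4.1.2) |
| Laboratory, by grade | not separately named | graded toxicities; shifts to post-baseline assessments | treatment-emergent grades; shifts to Day 7 (Tables 14.3.4.2, 14.3.4.3.1 to 14.3.4.3.3) |

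SAP section 5 defines descriptive statistics for continuous data as n, mean, median, SD, minimum and maximum, with no change score. Where the SAP wants change, its text says so: section 5.2.2 asks for change in viral titer and in daily activities.

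**2. How far the grades reach**

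I matched the analytes listed in SAP 5.3.3 to the DAIDS table in Protocol Appendix 16.2.

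- Chemistry: 21 listed, 15 graded. Not graded: direct bilirubin, blood urea nitrogen, chloride, gamma glutamyl transferase, LDH, protein.
- Hematology: 17 listed, 5 graded (hemoglobin, lymphocytes, neutrophils, platelets, leukocytes). Not graded: hematocrit, erythrocytes, the three erythrocyte indices, monocytes, basophils, eosinophils, and the four measures expressed relative to leukocytes.
- Total: 15 + 5 = 20 of 38 graded; 6 + 12 = 18 of 38 (47%) not graded.

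The DAIDS table does contain blood pressure criteria, but the SAP plans no graded output for vital signs. They would enter only through an event reported as an AE.

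**3. What by-visit means show and do not show**

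If every subject has both values, mean(Y − B) = mean(Y) − mean(B), so the mean change can be read from the by-visit table. The SD of the individual changes cannot, because it depends on the within-subject correlation r: with equal SD σ at both visits, SD(change) = σ√(2(1 − r)).

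If the later visit has only a subset S of the subjects:

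mean of Y in S − mean of B in all = (mean change in S) + (mean of B in S − mean of B in all)

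The last bracket is a difference in who was measured, not a change. For laboratory data at Day 14, the subset is formed by the Day 7 result (Protocol synopsis, 10.1.2.5, 11.2.1, 11.2.2). Protocol 10.1 lists Day 14 laboratory tests without that condition, but Table 1 schedules none.

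**4. Illustration of precision (r is assumed; the documents give none)**

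SE of mean change = σ√(2(1 − r)/n). SE of a difference of two unpaired means = σ√(2/n). The ratio is √(1 − r).

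- r = 0.5: √0.5 = 0.71, a 29% smaller SE.
- r = 0.7: √0.3 = 0.55, a 45% smaller SE.
- r = 0.8: √0.2 = 0.45, a 55% smaller SE.

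With the minimum of 80 elderly subjects, all with both values, the 95% half-width computed as unpaired is 1.96 × √(2/80) = 0.31 SD. The paired half-width is 1.96 × √(2 × 0.5/80) = 0.22 SD at r = 0.5 and 1.96 × √(2 × 0.2/80) = 0.14 SD at r = 0.8. With 120 subjects the figures are 0.25 SD against 0.18 and 0.11 SD.

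**The case against.** The strongest reply has five parts.

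- **Laboratory data do have a within-subject comparison.** A reader might infer that the SAP reduces them to unpaired summaries. It does not. Treatment-emergent abnormalities require a rise of at least one grade over the subject's own baseline, and the shift tables pair baseline with Day 7. The primary endpoint's own term is laboratory abnormalities, which these tables address. This stands, and it confines the laboratory half of the point to the continuous scale.
- **The commitment rests on the synopsis alone.** Its sentence speaks of qualitative analyses, and the SAP follows Protocol 13.9 closely for continuous summaries. This also stands: the protocol is uneven within itself. A reader might infer that section 6 hides a deliberate change. The documents show only that the difference was not declared.
- **Table titles are not table shells.** Table 14.2.9.1 does not mention change, yet SAP 5.2.2 plans it for daily activities. This cuts the other way: there the text supplies what the title leaves out, while in 5.3.3 and 5.3.4 the text is silent too.
- **Little would be hidden.** A reader might infer that a real shift in creatinine, neutrophils or blood pressure would be invisible. With complete data a mean shift shows in the by-visit means. Clinically significant laboratory results are also reported as AEs, and subject-level values are listed. This stands; the gap is in tabulation, not collection.
- **No decision hangs on precision.** No test is planned, and no standard error or interval is planned for these outputs. This stands, so the SE ratios are illustration only.

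**Conclusion.** The point holds, as a gap in tabulation and consistency. For vital signs and continuous laboratory values the SAP leaves out the change from baseline that the synopsis names, and does not declare it. Protocol 13.9 shares the omission.

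The gap is complete for vital signs, which have no within-subject output. For laboratory data it is partial: the grade-based tables cover 20 of 38 listed analytes, and only for movement across a grade boundary. What is lost is the spread of individual changes in all cases, and a same-subject comparison wherever values are missing or, at Day 14, collected selectively.

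The analyte count rests on the documents alone. The 29% to 55% smaller standard error rests on an assumed correlation of 0.5 to 0.8 and equal SDs at both visits; it is not a gain in the power of any planned test. A reader might also infer that change from baseline would isolate the effect of the drug. It would not: without a control group it mixes drug effect with recovery from influenza. It is still the paired contrast that the synopsis named.

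**What to change.** In SAP 5.3.3 and 5.3.4, add the within-subject change from baseline, by age group and overall, with n having both values, mean, SD, median, minimum and maximum:

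- Table 14.3.6 (vital signs): at Days 3, 7 and 14.
- Tables 14.3.4.1.1 and 14.3.4.1.2 (chemistry, hematology): at Day 7.
- Any Day 14 laboratory change: show it only as paired data, labelled as a subset selected on the Day 7 result.

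Use the baseline definition in SAP 3.3.8. State that for vital signs this is the Screening value, because the schedule of assessments has no vital signs in the pre-dose Baseline column. If the sponsor prefers not to add change, declare the departure from the synopsis in SAP section 6.

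The cost is SAP wording and extra rows in three tables. No new data are needed.
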